2.3 Sample size

Based on an extensive literature review (Table 1), we have conservatively estimated the six-month response rate for rheumatologist-led care to be 35%. Responders are defined according to the OMERACT-OARSI criteria (3).

The non-inferiority margin is set to 15 percentage points. To ensure adequate statistical power, a sample size of 400 patients (200 per arm) is required. This calculation assumes 80% power that a two-sided 95% confidence interval will demonstrate that OT-led care is not more than 15 percentage points inferior to rheumatologist-led care, given a response rate of 35% in both groups.

An assumed drop-out rate of 20% has been included in the sample size determination, based on observed attrition rates in comparable studies, typically ranging from 20% to 25%. Randomization will be stratified by center to account for inter-site variability.

More detailed information is available in the study protocol (2).

Publication	Type of intervention	Control group	Proportion of responders (intervention/control)			
			4 weeks	3 months	6 months	12 months
Østerås 2014 (4)	Hand exercises	Treatment as usual		46 % / 16%	30% / 28%	
Hennig 2015 (5)	Hand exercises	Treatment as usual		43% / 6%		
Dziedzic 2015 (6)	Joint protection	No joint protection		28% / 22%	42% / 27%	34% / 27%
Dziedzic 2015 (6)	Exercises	No exercises		26% / 24%	36% / 32%	38% / 34%
Wenham 2012 (7)	Prednisolone	Placebo	57% / 57%			

Table 1: Overview of the literature review used to estimate the expected number of responders.

STATISTICAL ANALYSIS PLAN for TASKSHIFT

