2.4.3 Decision Rule

Non-inferiority of treatment response rate is claimed if the null hypothesis is rejected on the significance level (alpha) of 0.025 (one-sided). That is, if the upper limit of the two-sided 95% confidence interval for the treatment difference (probability of response under RT minus OT management) is less than 15%.

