5.1.4 Overview of Outcomes

Level	Outcome	Timeframe	Type
Primary	OMERACT/OARSI response (3)	182/364 days	Dichotomous
	EQ-5D-5L (8)	182/364 days	Discrete/Continuous
Safety	Adverse events	182 days	Discrete

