5.2 Analysis Methods

5.2.1 Primary Outcome

5.2.1.1 Primary Analysis

For the analysis of the primary outcome, a logistic regression with treatment provider as independent and OMERACT/OARSI responder classification (3) as dependent variable will be conducted, adjusting for treatment center (the stratification factor used in the randomization). Response probability as well as risk difference will be calculated using the adjusted risk and risk difference estimators (9) using bootstrapping to estimate standard errors to form normal based 95%

STATISTICAL ANALYSIS PLAN for TASKSHIFT

confidence intervals. As a sensitivity analysis, an analysis will also be carried out adjusting for baseline pain, disease activity and function.

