5.2.1.2 Additional analysis

For the analysis of cost-effectiveness, the total cost-effectiveness will be calculated as total health effect of the two strategies. The outcome of interest is the incremental cost-effectiveness ratio (ICER), which is defined by the incremental cost (ΔC = cost OT-led OA management – cost of rheumatologist-led OA management) per incremental QALY (ΔU = QALYs with OT-led OA – cost of rheumatologist-led OA). If the cost-per-QALY of the ICER is less than the cost-effectiveness acceptability threshold, the OT-led OA management may be considered a cost-effective alternative to the rheumatologist-led OA management. This criterion is usually summarised in the net-monetary benefit static:

(1) $NMB = W * \Delta U - \Delta C$, where W is the acceptability threshold value, and ΔU is the incremental utilities/QALYs gained and ΔC is the incremental cost. If the NMB is positive ($NMB > 0$), the new programme is considered to have acceptable cost-effectiveness for the decision maker, otherwise not.

As there is no current official acceptability threshold value (W), we will follow the approach of the Norwegian Medicines Agency (10) to calculate an absolute prognosis loss for the patients under the current treatment strategy. This static has been discussed in the official White Paper on priority setting and is often used as a proxy for the upper limit of willingness to pay per QALY, also known as the cost-effectiveness acceptability threshold.

Healthcare costs are a function of resource use and the unit cost of those resources. In this study, resource use is defined as the number and type of contact with healthcare personnel, administered treatment (such as injections or surgical interventions) and assistive devices, patient education and exercise options as well as work absence, taking a healthcare perspective. We will use official tariffs and rates as unit costs in valuing the resource use.

To calculate QALYs, we follow the recommended approach by the Norwegian Directorate of Health (11). The patients' description of their own health is taken from the collected EQ-5D data. These scores are subsequently weighted with preference weights from the general population. In the absence of a survival-effect from treatment, the calculated utility of health will serve as the measure of the QALY.

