Finally, we will use non-parametric bootstrapping to assess the degree of uncertainty around the likelihood of cost-effectiveness (12). This allows assessing uncertainty without having to impose parametric assumptions on our highly skewed data. We will perform 10,000 bootstrap samples with replacement of the sample outcomes. For each bootstrapped sample replica, we calculated the net monetary benefit (1) using the assumed acceptability threshold (W). The likelihood of cost-effectiveness will then be calculated as the proportion of all bootstrapped samples in which OT-led OA management conferred a positive net monetary benefit.

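### The cost-effectiveness analysis names no adjustment for baseline health state or centre; adding it would cost almost nothing and would make the QALY difference more precise and less exposed to chance imbalance

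*SAP*

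**What the plan says.** Section 1.2.1 makes cost-effectiveness one of the primary objectives. Section 5.2.1.2 defines ΔC and ΔU as OT-led minus rheumatologist-led. (The second term of ΔU is printed as a cost; I read it as QALYs.) Both go into NMB = W × ΔU − ΔC, and a positive value counts as acceptable cost-effectiveness.

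For QALYs, the patients' EQ-5D answers are used: "These scores are subsequently weighted with preference weights from the general population". With no survival effect, the resulting utility serves as the QALY. Uncertainty is handled by the bootstrap: "We will perform 10,000 bootstrap samples with replacement of the sample outcomes". The NMB formula is then applied in each replicate. Section 5.2.1.5 adds that the economic analysis will use imputation, without giving a model.

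No regression, covariate or stratum is named for QALYs, costs or NMB. For the responder outcome, by contrast, section 5.2.1.1 specifies a logistic regression "adjusting for treatment center (the stratification factor used in the randomization"), with a sensitivity analysis adding baseline pain, disease activity and function. Section 5.2.1.6 ties that baseline adjustment to the response rate. The EQ-5D-5L row of the table in section 5.1.4 reads "182/364 days Discrete/Continuous", with no baseline entry.

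**The concern.** The SAP states adjustment where it wants it, for the responder outcome, and states none for the economic outcome. Taken as written, ΔU and ΔC are plain differences between arms.

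Section 5.2.1.2 takes the utility itself as the QALY, so the outcome is a level of health. An arm that happens to start in better health will tend to stay somewhat better, and a plain difference credits that part to the care model. Baseline utility would usually also explain a good share of the variation in follow-up utility. Leaving it out widens the bootstrap distribution, which, for a given point estimate, pulls the likelihood of cost-effectiveness toward 50%. What is at stake is precision, and protection against whatever imbalance this one randomisation produces, for a primary objective judged by the sign of NMB.

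**Working it through.** **Number of completers.** The SAP gives no figure for the economic analysis, so I take the arm size from section 2.3. There, "The non-inferiority margin is set to 15 percentage points", with "80% power that a two-sided 95% confidence interval will demonstrate" non-inferiority, "given a response rate of 35% in both groups".

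- n per arm = (1.960 + 0.8416)² × 2 × 0.35 × 0.65 / 0.15² = 7.849 × 0.455 / 0.0225 = 158.7, so 159.
- With 20% drop-out: 159 / 0.80 = 198.75, so 199, against the stated 200. The plan's figure reproduces.
- Completers: 200 × 0.80 = 160 per arm.

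**Assumptions (not in the SAP).** Utility SD 0.20 at every time point; the same correlation ρ between any two time points, with ρ = 0.4, 0.5 and 0.7. The percentage variance cuts below depend on ρ only, not on the SD or arm size.

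**Chance baseline difference.** SE = 0.20 × √(2/160) = 0.0224. If imputation keeps 200 per arm, it is 0.20 × √(2/200) = 0.0200.

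**Case A: QALY based on a single follow-up utility.** The share of a baseline difference that passes into ΔU is ρ. The variance left after adjustment is 1 − ρ².

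| ρ | Share passed on | ΔU shift at a 1-SE imbalance | Variance left | Variance cut |
|---|---|---|---|---|
| 0.4 | 0.40 | 0.40 × 0.0224 = 0.009 | 0.84 | 16% |
| 0.5 | 0.50 | 0.50 × 0.0224 = 0.011 | 0.75 | 25% |
| 0.7 | 0.70 | 0.70 × 0.0224 = 0.016 | 0.51 | 49% |

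The upper end of the cut is 49% at ρ = 0.7 (1 − 0.51), and 51% is the variance that remains there. The range of cuts in Case A is therefore 16% to 49%.

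**Case B: QALY as area under the curve at 0, 6 and 12 months.** Weights are 0.25, 0.5 and 0.25. In units of SD²:

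- variance = 0.375 + 0.625ρ
- covariance with baseline = share passed on = 0.25 + 0.75ρ
- proportion of variance removed = (0.25 + 0.75ρ)² / (0.375 + 0.625ρ)

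| ρ | Variance | Share passed on | Variance cut | SE of ΔU, unadjusted | SE of ΔU, adjusted |
|---|---|---|---|---|---|
| 0.4 | 0.6250 | 0.550 | 48% | 0.0177 | 0.0127 |
| 0.5 | 0.6875 | 0.625 | 57% | 0.0185 | 0.0122 |
| 0.7 | 0.8125 | 0.775 | 74% | 0.0202 | 0.0103 |

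**Simulation of Case B.** 4,000 trials per scenario, 160 per arm, SD 0.15 or 0.20, ρ 0.4 or 0.6, true ΔU = 0. Among trials in which the OT arm started more than 1 SE worse, unadjusted ΔU averaged −0.014 to −0.023 and was positive in 3% to 10%. Adjusted ΔU averaged about 0 and was positive in 47% to 54%.

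**Step to NMB.** Var(NMB) = W² Var(ΔU) + Var(ΔC) − 2W Cov(ΔU, ΔC). The SAP gives no W, cost SD or cost–QALY correlation, so the gain in ΔU cannot be turned into a gain in NMB.

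**The case against.** The strongest reply is that nothing here is wrong. Under 1:1 randomisation the plain difference is unbiased, and an ordinary bootstrap already includes the variability due to chance baseline differences. That stands. What remains is lost precision, and error conditional on the imbalance that actually occurs, which the bootstrap does not recentre.

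It can also be said that the SAP never calls the analysis unadjusted, and that it cites outside guidance for QALYs and for the bootstrap. Those sources are not at hand and might add something. But the SAP should fix the analysis itself, and it names adjustment only for the responder outcome.

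Several stronger readings are tempting and are not supported:

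- A reader might infer that baseline imbalance passes in full into ΔU. The share is about 0.4 to 0.78 for the correlations assumed.
- A reader might infer that imbalance decides the sign of NMB. The calculation shows this only where ΔC is near 0.
- A reader might take 48% to 74% as the expected gain. Those figures need a QALY that includes baseline utility, and section 5.1.4 lists only days 182 and 364.
- A reader might see centre imbalance as a threat. Section 2.2 uses a separate list per centre with blocks of 10, so centre is nearly balanced; adjusting for it serves precision and consistency with 5.2.1.1.
- A reader might contrast a change-based responder outcome with a level-based utility. The SAP gives only a yes/no coding and leaves the detail to the protocol.

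The SAP chose non-parametric resampling because the data are skewed. A regression refitted in each replicate is compatible with that, since its uncertainty comes from the resampling and not from a normal error model.

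**Conclusion.** The point holds as an improvement in efficiency and in protection from chance imbalance, not as a correction of an invalid analysis. As written, ΔU and ΔC are unadjusted. For ρ of 0.4 to 0.7, adjusting for baseline utility leaves 84% to 51% of the variance of ΔU for a single follow-up utility, and removes 48% to 74% for an area-under-the-curve QALY. At ρ = 0.5 in the latter case the SE falls from 0.0185 to 0.0122, given SD 0.20 and 160 per arm. These sizes rest on assumed values and on baseline EQ-5D-5L having been collected. With baseline pain, disease activity and function as substitutes, the gain depends on their unknown correlation with utility. The effect on NMB and on the likelihood of cost-effectiveness cannot be sized from the SAP.

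**What to change.** In section 5.2.1.2, state that in each of the 10,000 replicates:

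1. patients are resampled within arm and centre, with each patient's cost and QALY kept together;
2. ΔU is the arm coefficient from a regression of QALYs on arm, centre and baseline EQ-5D-5L utility or, if that was not collected, on arm, centre and baseline pain, disease activity and function;
3. ΔC is the arm coefficient from a regression of costs on arm and centre;
4. NMB is computed from these two values.

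State in section 5.1.4 whether a baseline EQ-5D-5L value exists, and say how the imputation in section 5.2.1.5 combines with the bootstrap. The unadjusted result can be kept as a sensitivity analysis. The cost is SAP wording and a few lines of code, with no new data. It is best settled before the results by arm are seen, so that the choice of adjustment cannot depend on them.

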5.2.1.3 Summary Measures

See 5.1.1

5.2.1.4 Assumption Checks and Alternative Analyses

A logistic regression includes the following assumptions:

STATISTICAL ANALYSIS PLAN for TASKSHIFT

- Binary dependent variable: This assumption is fulfilled via the study design.
- Independence: This assumption is fulfilled via the study design.
- No severe multicollinearity: This assumption is fulfilled via the study design.
- Sufficient number of observations: We are expecting a rate of approximately 35% responders, which would provide a sufficient number of patients per group.

5.2.1.5 *Missing Data*

We are expecting the amount of missing data to increase with time, but we cannot retrace the individual reasons for missingness. The primary analysis will be based on complete case analysis, whereas the cost-efficiency analysis will utilize imputation.

5.2.1.6 *Sensitivity Analyses*

If deemed necessary, sensitivity analyses will be conducted to address missing data, if needed also on subgroup data. Further, analyses adjusted for baseline status of disease activity, pain and function will be conducted to evaluate a possible effect on response rate within the two treatment arms.

5.2.1.7 *Subgroup Analyses*

No subgroup analyses are planned outside of the sensitivity analyses.

5.2.2 *Continuous Secondary Outcomes*

5.2.2.1 *Main Analysis*

To identify clinically relevant predictors for symptom improvement 6 and 12 months after baseline, we will fit a regression model and select variables based on standardized beta-values as well as clinical usefulness based previous research and clinical relevance.

5.2.2.2 *Summary Measures*

See 5.1.1

5.2.2.3 *Assumption Checks*

Regression models entail four key assumptions:

- Independence: Given the study design, we are confident that this assumption is met.
- Linear relationship: If this assumption is violated, we will apply a logarithmic transformation.
- Normality: If this assumption is violated, we will apply a logistic transformation

STATISTICAL ANALYSIS PLAN for TASKSHIFT

- Homoscedasticity: If this assumption is violated, we will apply a logistic transformation to the dependent variable or explore alternative options depending on the data characteristics.

5.2.2.4 *Missing Data*

Same as 5.2.1.4

5.2.2.5 *Sensitivity Analyses*

Same as 5.2.1.5

5.2.2.6 *Subgroup Analyses*

Same as 5.2.1.6

5.2.3 Additional Analyses

5.2.3.1 *Exploratory Analyses*

The following additional, hypothesis-generating exploratory analyses will be conducted in addition to the above-stated analyses. If during the course of the data analyses additional questions will be raised, we will add them to this list of exploratory analyses.

- 1) To explore the potential influence of disease activity on treatment response, we will compare participants with erosive hand OA to those with less active inflammation, as defined by Xray scorings. Comparative analyses as well as additional regression models will be calculated for this.
- 2) To explore associations between different disease-related factors, we will investigate the relationships between various factors using correlation analyses.
- 3) To understand the disease trajectory of the participants, we will explore time and treatment dependent changes in different disease-related factors and compare these between the groups using comparative statistics and regression models.

6 Safety Analyses

6.1 Adverse Events/Safety

The main considerations in this study relate to safety and non-inferiority. Since this study does not include novel interventions, we are not expecting any adverse events connected to the study design. We will therefore focus on the safety aspects of the two treatment approaches and evaluate them in

STATISTICAL ANALYSIS PLAN for TASKSHIFT

the health economics section of the analysis. For both groups the healthcare usage (including additional contact to healthcare professionals as well as supportive devices) related to hand OA between baseline and six months as well as twelve months will be registered, compared and used to evaluate cost-effectiveness.

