5.1.3 Secondary Outcomes Definitions

The number of painful joints, function (measured by the MAP-hand questionnaire) and hand strength (measured by JAMAR dynamometer) will be reported at baseline and 6 months. Information about adverse events will be collected from patients' medical records and used in the evaluation of safety.

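### Adverse events are the SAP's only listed safety outcome, yet section 6.1 sends the safety evaluation to health economics and leaves them without a by-arm analysis

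*SAP*

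**What the plan says.** Section 5.1.4 of the SAP has a single row at safety level: "Adverse events 182 days Discrete". Section 5.1.3 states the source and purpose of these data: "Information about adverse events will be collected from patients' medical records and used in the evaluation of safety".

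Section 6.1, headed for adverse events and safety, opens with "The main considerations in this study relate to safety and non-inferiority". It continues: "Since this study does not include novel interventions, we are not expecting any adverse events connected to the study design". The next sentence runs over a page break: "We will therefore focus on the safety aspects of the two treatment approaches and evaluate them in" and then "the health economics section of the analysis". The rest of 6.1 says that hand-OA-related healthcare use, up to six and twelve months, will be recorded in both groups, compared, and used for cost-effectiveness.

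The health economics methods are in 5.2.1.2. They cover resource use, unit costs, QALYs, the ICER, net monetary benefit and a bootstrap of the probability of cost-effectiveness.

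**The concern.** A reader who wants to know how adverse events will be analysed goes to 6.1, is sent on to health economics, and finds nothing about adverse events there. The only outcome listed for safety is therefore to be collected but has no stated summary, denominator, effect measure or comparison.

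What 6.1 does specify is a different measure. Healthcare use can carry some information on harm, because additional contacts, injections or surgery may follow from inadequate care. Its direction is ambiguous, however. More contacts can mean complications or attentive follow-up; fewer can mean good control or a problem that nobody picked up. Within the net monetary benefit, lower use lowers cost and so counts in favour of the arm that has it. The measure is also limited to use related to hand OA, so an event recorded under another label would not appear.

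At stake is whatever the report says on safety. Section 1.1 names safety among the things to be evaluated when tasks are shifted, and 6.1 ranks it with non-inferiority. A statement on safety could then rest on a cost measure, without the data that the SAP lists for the purpose.

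**Working it through.** The main check is a reading of every place in the SAP where an adverse-event analysis could stand.

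| SAP section | What it provides on safety |
|---|---|
| 5.1.3 | Adverse events from medical records, to be used in evaluating safety |
| 5.1.4 | Adverse events as the only safety-level outcome, 182 days, discrete |
| 5.2.1.2 | Contacts, treatments, devices, education and exercise, work absence, costs and QALYs; no adverse events |
| 5.2.2 | Regression for predictors of symptom improvement; no adverse events |
| 5.2.3 | Exploratory analyses of disease activity, associations and trajectories; no adverse events |
| 6.1 | Refers safety to health economics; compares healthcare use only |
| 6.2 | Laboratory values collected at baseline to check exclusion criteria |

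Sections 5.1.3 and 5.1.4 promise an evaluation. Section 6.1 states a method that does not use the promised data, and the section it points to does not use them either. Section 6.1 does not refer the matter to the protocol.

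The SAP states no adverse-event figure, so there is none to reproduce. The arm size used below, 200, comes from section 2.3 and is not in dispute. With 35% response in both arms, a 15-point margin, one-sided alpha 0.025 and 80% power, n = (1.960 + 0.842)² × 2 × 0.35 × 0.65 / 0.15² gives 159 per arm. Then 159 / 0.80 gives 199 per arm, or 398 in total against the stated 400.

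Two illustrations show what an adverse-event table could and could not say.

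1. Zero events in one arm. The exact two-sided 95% upper limit is 1 − 0.025^(1/n). For n = 200 it is 1.83%; for n = 160 (200 less 20% drop-out) it is 2.28%.
2. Risk difference with the same assumed rate p in both arms. The half-width of the 95% CI is 1.96 × √(2p(1 − p)/n).

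| Assumed p | n = 200 per arm | n = 160 per arm |
|---|---|---|
| 2% | 2.7 points | 3.1 points |
| 5% | 4.3 points | 4.8 points |
| 10% | 5.9 points | 6.6 points |

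The rates are assumptions. The column for 160 is a lower case only: the drop-out rate in 2.3 belongs to the primary outcome and does not settle the denominator for events read from medical records.

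**The case against.** The strongest defence is that 6.1 speaks only of events connected to the study design. On that reading it sets aside harm from trial procedures and keeps the safety of care in both arms in view, with the events of 5.1.3 as input. Nothing in 6.1 withdraws 5.1.3. This is a fair reading of the sentence, but it does not supply the analysis: 6.1 sends the evaluation to health economics, and 5.2.1.2 has no place for adverse events.

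Other parts of the defence stand and limit the point.

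- A reader might infer that the SAP drops an adverse-event comparison. It does not, because none was ever specified. The analysis is absent, and the sections do not agree.
- A reader might take 182 days against six and twelve months as a contradiction. It is not one: the horizons belong to different measures, and 5.1.4 itself follows EQ-5D-5L to 364 days.
- A reader might conclude that healthcare use says nothing about harm. That is too strong; it is an incomplete proxy.
- Safety is not among the objectives in 1.2, and the SAP sets no safety hypothesis or decision rule. The obligation comes from 5.1.3, 5.1.4 and 6.1 themselves.
- Nothing in the SAP shows that seriousness or relatedness is recorded, so tables by those categories cannot be assumed to be available.

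The protocol may well define adverse events and how they are collected. Analysing an outcome that the SAP lists is still the SAP's task. That the care is low-risk argues for a simple table, not for having none.

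**Conclusion.** The point holds in this limited form. The only safety outcome listed in 5.1.4 has no by-arm analysis anywhere in the SAP, and 6.1 names a method, the comparison of healthcare use, that does not fit what 5.1.3 says the adverse-event data are for. This should be corrected. It does not touch the primary analysis or the sample size.

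No numerical size can be attached from the SAP, since it gives no event rate. The illustrations show only that expecting few events does not make a table redundant: even zero events among 200 patients is compatible with a true rate of up to about 1.8%, and a comparison at assumed rates of 2% to 10% would have a half-width of roughly 3 to 6 points at 200 per arm.

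The documents do not support the stronger inference that harm in one arm would in fact be hidden or turned into a cost saving. They show only that the plan as written has no analysis by which a difference in adverse events would be seen.

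**What to change.** In 6.1, add a table by randomised arm of the number and percentage of patients with at least one adverse event to 182 days, with the risk difference and its 95% CI. State the denominator; section 3.3 defines only one analysis set, the full analysis set. Choose an interval method suited to small counts, because a simple normal-approximation interval has zero width if neither arm has an event. Report the table separately from the economic analysis.

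Show serious or related events only if the collected data already classify them. Keep healthcare use as a cost input in 5.2.1.2 and, at most, as supportive information on safety. Reword the reference to health economics in 6.1 so that it agrees with 5.1.3 and 5.1.4.

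The cost is a few sentences in the SAP and one table from data already planned for collection. No design element changes.
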